8.5.1.1 Dose Unit Conversion

All exposure tables and listings will display dose administered in MBq. Dose recorded in mCi will be converted to MBq as follows:

$$MBq = 37 \times mCi$$

8.5.2 Treatment Emergent Adverse Events

A summary of TEAEs will be reported in the tables including number of all TEAEs and number of subjects who experienced at least one TEAE. The summary of TEAEs will be broken down further in descending frequency by SOC and PT, and by PT only in separate tables. A subject will be counted once if the subject reported one or more events in a given level of summarization.

All AEs (regardless of treatment emergence) will be presented in a listing.

8.5.2.1 Severity

TEAE severity will be reported in a table in the same manner as outlined in 8.5.2. Events recorded with missing intensity will be summarized as 'Severe'. If the same TEAE is reported more than once for a subject within an SOC/PT, the TEAE with the worst severity will be summarized in the table.

8.5.2.2 Relationship to Flortaucipir

TEAE relationship to flortaucipir will be reported in a table in the same manner as outlined in 8.5.2. TEAEs with a missing relationship to flortaucipir will be summarized as 'Related' to flortaucipir. If the same TEAE is reported more than once for a subject within an SOC/PT, the TEAE most related to flortaucipir will be summarized in the table.

8.5.2.3 Relationship to Study Procedure

TEAE relationship to study procedure will be reported in a table in the same manner as outlined in 8.5.2. TEAEs recorded with a missing relationship to study procedure will be regarded as

related to study procedure. If the same TEAE is reported more than once for a subject within that SOC/PT, the TEAE most related to study procedure will be summarized in the table.

8.5.2.4 Serious Adverse Events

Serious TEAEs will be summarized in a similar manner as described in Section 8.5.2. TEAEs recorded with a missing seriousness will be summarized as ‘Serious’. If more than one serious TEAE was reported for a subject with the same SOC or PT, the TEAE will be counted only once in that SOC or PT.

8.5.2.5 Adverse Events Leading to Study Discontinuation

TEAEs leading to study discontinuation will be summarized in a similar manner as described in section 8.5.2.

8.5.2.6 Adverse Events Leading to Death

TEAEs leading to death will be summarized in a similar manner as described in section 8.5.2.

8.5.2.7 Missing and Partial AE Onset Dates

If the AE onset dates are missing, then the most conservative approach will be used to decide if the AE is TEAE or not, as detailed in the table below:

Table 4: Imputation Algorithm for Missing AE Date/Time

Scenario	Imputation
Missing AE start date/time	if AE stop date is missing or after injection date, then TEAE =‘Y’. If AE stop date is prior to the injection date, then TEAE=‘N’
Missing AE start time	Impute time as 23:59, and follow TEAE definition in section 6.6.2
Partial Date	
If AE start day is missing then:
 
 If AE start month and year are the same as injection date month and year then TEAE=‘Y’, otherwise impute missing days as the first day of the respective AE start month, and follow TEAE definition in section 6.6.2 
If AE start month is missing then:
 
 If AE start year is the same as injection year then TEAE=‘Y’, otherwise TEAE = ‘N’

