7.7.2. Adverse Event Definitions

Adverse Events

An adverse event is any undesirable experience occurring to a subject during a clinical trial, whether or not considered related to the study drug.

For reporting purposes, Avid will distinguish among pre-existing conditions, trial-emergent adverse events and treatment-emergent adverse events.

Pre-existing conditions (i.e., undesirable experiences, signs or symptoms that begin prior to the Screening Visit) will be recorded on the medical history eCRF pages. During the study, site personnel will record any change in the condition(s) and occurrence and nature of any AEs. Signs and symptoms that are believed to be due to the pre-existing condition under study (started prior to dose of study medication) do not have to be recorded in the AEs section of the eCRF, unless there is an increasing in frequency and severity.

Trial-emergent adverse events are undesirable experiences, signs or symptoms that begin, or worsen in intensity or frequency, after the informed consent, and prior to administration of study drug (^{18}F -AV-1451) at the imaging visit. These will be recorded on the adverse event eCRFs.

Treatment-emergent adverse events are undesirable experiences, signs, or symptoms associated with the use of a study drugs. For the purposes of this study an adverse event will be considered associated with the use of ^{18}F -AV-1451 if it begins or worsens in intensity or frequency within 48 hours after the administration of ^{18}F -AV-1451. Adverse experiences that occur after administration of study drug but outside the 48 hour reporting window will not be reported unless the investigator believes they are attributable to the drug.

The end of study for the purpose of adverse event reporting is defined as 48 hours after the administration of ^{18}F -AV-1451 Injection.

Serious Adverse Event (SAE)

A SAE is an AE that results in one of the following outcomes or constitutes one of the following events:

- Death;
- Initial or prolonged inpatient hospitalization (other than that required by protocol; “social hospitalization” or any hospitalization for non-medical reasons does not constitute a SAE);
- A life-threatening experience (that is, immediate risk of dying);
- Persistent or significant disability/incapacity;

- Congenital anomaly/birth defect;
- Considered significant by the investigator for any other reason.

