4.1.3 Follow-Up Phone Call

A follow-up phone call to the subject, or designated decision maker, was conducted between 2 and 3 business days after imaging day, but not before 48 hours post-injection, to confirm subject well-being and to collect information about any new adverse events. If both of these days were not business days, the follow-up phone call occurred the following business day.

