4.4 Determination of Sample Size

No power or sample size calculation was done for this study as there was no hypothesis for testing per study objectives. Approximately 179 subjects including healthy controls and subjects at risk for tau accumulation as defined by the sites' companion protocols were dosed with flortaucipir and underwent a PET scan.

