6.6 Safety Assessments

6.6.1 *Extent of Exposure and Compliance to Study Treatment*

During the flortaucipir imaging sessions, all subjects received a single IV bolus administration target dose of 240 (6.49 mCi) or 370 MBq (10 mCi) of flortaucipir injection.

6.6.2 *Adverse Events*

An AE is any undesirable experience occurring to a subject during a clinical trial, whether considered related to the study drug or not. AEs are classed by severity and seriousness.

Treatment-emergent adverse events (TEAE) are any untoward medical occurrences associated with the use of a drug in humans. For the purposes of this study, untoward medical occurrences will be considered associated with the use of flortaucipir, and thus be reported as TEAEs, if they occur within 48 hours after administration of the PET tracer. The end of study for the purpose of AE reporting is defined as 48 hours after the administration of flortaucipir injection.

The investigator's verbatim term of both serious and non-AEs will be mapped to system organ class (SOC) and preferred terms (PT) using the Medical Dictionary for Regulatory Activities (MedDRA) Version 17.1.

Investigators will be instructed to report their assessment of the potential relatedness of each AE to protocol procedure and flortaucipir. The assessment of the relationship of an AE to the administration of the flortaucipir is a clinical decision based on all available information at the time of the completion of the eCRF.

Investigators will also assess the severity of AE. Severity is classified as mild/moderate/severe (increasing severity).

Serious AEs (SAEs) are events that result in one of the following outcomes or constitute one of the following events:

- Death
- Initial or prolonged hospitalization (other than that required by protocol; "social hospitalization" or any hospitalization for non-medical reasons does not constitute an SAE)
- A life-threatening experience (that is, immediate risk of dying)
- Persistent or significant disability/incapacity
- Congenital anomaly/birth defect
- Considered significant by the investigator for any other reason

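### Imputing a missing AE start time as 23:59 classes every untimed event dated the second day after injection as non-TEAE, contrary to the SAP's stated conservative aim

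*SAP*

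**What the plan says.** SAP 6.6.2 counts events as treatment-emergent "if they occur within 48 hours after administration of the PET tracer". The limit is in hours, and the SAP definition has no exception for later events that the investigator attributes to the drug.

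SAP 8.5.2.7 deals with incomplete onset information. It states that "then the most conservative approach will be used to decide if the AE is TEAE or not" and refers to Table 4, titled "Imputation Algorithm for Missing AE Date/Time". For a missing start time the table says "Impute time as 23:59, and follow TEAE definition in section 6.6.2". The row does not distinguish the injection date from later dates.

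The other rows lean towards inclusion. With the start wholly missing, the event is a TEAE unless its stop date precedes injection. With only the day missing, it is a TEAE if the month is the injection month; in any other month the first day is imputed, which is the earliest choice. Missing severity, relationship and seriousness also default to the worst case (SAP 8.5.2.1 to 8.5.2.4).

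The AE summary tables in SAP 8.5.2 count TEAEs only. For everything else, "All AEs (regardless of treatment emergence) will be presented in a listing".

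**The concern.** A single late clock time cannot be conservative at both ends of a 48-hour window. At the start, 23:59 pushes an untimed injection-day event past the injection and so into the window. At the end, it pushes an untimed second-day event out, even when the true onset could have been hours before the limit.

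The result is also inconsistent within the table. An event known only to have started in the injection month is a TEAE. An event known to have started on the second day, with only the clock time missing, is not.

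Expanding the safety database is one of the study's two primary objectives. An affected event would drop out of the overall TEAE summary and of the breakdowns by severity, relationship, seriousness, discontinuation and death. The situation is plausible: second-day events begin after discharge, and the planned contact is a call made "but not before 48 hours post-injection, to confirm subject well-being and to collect information about any new adverse events", so onset is recalled rather than observed.

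**Working it through.** **Inputs.** TEAE window: 0 to 48 hours after injection (SAP 6.6.2). Imputed time: 23:59, that is 23.98 h (SAP Table 4). Subjects dosed: about 179 (SAP 4.4). The documents give no injection clock times; 09:00 and 17:00 are assumed as illustrations. The plan gives no figure of its own to reproduce.

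**Step 1: apply the rule.** Let *i* be the injection time in hours after midnight on day 0, *d* the calendar day of AE onset and *t* the imputed time. Elapsed time = 24*d* + *t* − *i*, and the event is a TEAE if 0 ≤ elapsed ≤ 48.

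With *t* = 23.98:
- Day 0: 23.98 − *i*, never negative, so TEAE.
- Day 1: 47.98 − *i*, never above 48, so TEAE. This is correct whatever the true time.
- Day 2: 71.98 − *i*, above 48 unless *i* is 23:59. For 09:00, 71.98 − 9 = 62.98 h; for 17:00, 71.98 − 17 = 54.98 h. Non-TEAE.
- Day 3: 95.98 − *i*, always above 48. Non-TEAE, correctly.

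**Step 2: check every injection minute of the day.** Number of the 1,440 possible injection minutes for which an untimed event is classed as a TEAE:

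| Onset date | 23:59 on all dates (SAP) | 00:00 on all dates | 23:59 on injection date, 00:00 on others |
|---|---|---|---|
| Day −1 | 0 | 0 | 0 |
| Day 0 | 1,440 | 1 | 1,440 |
| Day 1 | 1,440 | 1,440 | 1,440 |
| Day 2 | 1 | 1,440 | 1,440 |
| Day 3 | 0 | 0 | 0 |

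The single day-2 exception under the SAP rule is an injection at exactly 23:59, which is not realistic for an imaging visit. A blanket 00:00 would merely move the problem to the injection date. The split rule changes day 2 only.

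**Step 3: how much of day 2 is in the window.** The window closes on day 2 at the injection clock time, so the in-window share of that day is *i*/24: 9/24 = 37.5% for 09:00 and 17/24 = 70.8% for 17:00. The rest, 62.5% and 29.2%, lies beyond 48 hours. These are shares of clock time. They become shares of events only if onset is uniform over the day, which is an assumption.

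**Step 4: size per event.** Over the whole safety population one event changes an incidence by at most 1/179 = 0.56 percentage points, and by nothing if the subject is already counted in that row. If the tables are also split by diagnostic group (Protocol 8.1), the denominator is smaller; the documents give no group sizes.

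**The case against.** The lead-in to Table 4 speaks of missing onset dates, and here the date is known, so one could say that the conservative aim was never promised for this row. That is a fair reading of one clause. But the sentence refers to the table as a whole, the table's title covers times, and the row sits in it. The contradiction stands.

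Missing times may be rare. Protocol 7.7 asks for start and stop times (the shorter example list in 7.7.3 omits time but does not waive it), and Protocol 10.6 has a monitor verify the eCRF against source. Recall at a phone call does not show that times are in fact missing. This stands, and the count may be zero. Nor is any event lost altogether: all AEs are listed, and SAEs have a separate 24-hour reporting route (Protocol 7.7.4).

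A reader might go further and infer a conflict with Protocol 7.7.2, under which events "outside the 48 hour reporting window will not be reported unless the investigator believes they are attributable to the drug": a recorded second-day event would then probably have been judged in-window or drug-related by the site. The documents do not support that. The protocol text governs what sites report, whereas Table 4 classifies what has been recorded. Protocol 10.7 asks for all AEs encountered during the trial to be documented, and the call at or after 48 hours collects any new events, so later onsets could be recorded too. An attributed event that began after 48 hours is not a TEAE under SAP 6.6.2 in any case.

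A reader might also infer that most affected events are truly in-window. The documents do not show this either. With a morning injection the in-window part of day 2 is largely overnight; if fewer onsets are noted then, the share is below 37.5%.

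**Conclusion.** The rule does not do what the SAP says it does. For any realistic injection time, every untimed AE dated the second calendar day after injection becomes non-TEAE, although part of that day is inside the window, and nothing else in either document recovers it. That result needs no assumption beyond an injection before 23:59.

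The severity is minor. The number of affected events cannot be estimated from the documents. The AE analysis is descriptive, so only reported incidence is touched, not a test. SAP 4.4 describes subjects as already dosed ("Approximately 179 subjects including healthy controls and subjects at risk for tau accumulation"), so the sponsor can count the affected records directly. The in-window shares are illustrations that rest on assumed injection times and uniform onset.

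**What to change.** Replace the missing-time row of Table 4 with:

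*Missing AE start time: if the start date is an injection date, impute 23:59; on any other date impute 00:00. Then apply the TEAE definition in section 6.6.2 to each injection; TEAE = Y if any injection qualifies.*

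The per-injection wording covers subjects with two imaging sessions (SAP 4.1.4). A stop-date condition is deliberately left out: it would also move some untimed injection-day events from Y to N, which is a separate change. Without it, only untimed second-day events change class.

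The cost is one table row and a few lines of program code. The downside is that some second-day events that began after 48 hours will be counted as TEAEs: under the assumptions in the working, about 29% of such records for a 17:00 injection and about 62% for a 09:00 injection. The stated conservative aim accepts that error in preference to the opposite one. The sponsor should also report how many records the change affects.

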4.1.2 Flortaucipir PET Imaging Visit

For the flortaucipir PET imaging session, an intravenous (IV) catheter was placed for administration of flortaucipir injection. Subjects received a single IV bolus injection target dose of 240 megabecquerel (MBq) (6.49 millicuries (mCi)) or 370 MBq (10 mCi) of flortaucipir injection. Vital signs were taken in a supine position immediately prior to (within 30 minutes of) flortaucipir injection and at the completion of imaging prior to subject discharge. At approximately 80 minutes post injection, a 20-minute dynamic brain scan was obtained. Sites may have elected to use an alternative imaging protocol (i.e. different scan duration or scan start time) with additional time points with sponsor approval. All datasets were submitted to the sponsor for analysis.

Adverse events (AE) were continuously monitored during the imaging visit (see section 6.6.2). Any subject who experienced an adverse event was not discharged until the event had resolved or stabilized.

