7.2 Handling of Dropouts or Missing Data

Dropout subjects will not be replaced in this study. For situations with no rules for handling missing data the default will be no imputation.

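### SAP Table 4 flags AEs with a partial start date as treatment-emergent even when the recorded stop date is before injection, and its missing-start-date row has no branch for a stop on the injection date

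*SAP*

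**What the plan says.** SAP 6.6.2 counts an AE as a TEAE when it occurs in the 48 hours following the injection. SAP 8.5.2.7 covers AEs whose onset date is missing or partial. It states that "then the most conservative approach will be used to decide if the AE is TEAE or not, as detailed in the table below". Table 4 then has three rows:

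- **Start date and time missing.** The flag is Y under the condition "if AE stop date is missing or after injection date, then", and N under the condition "If AE stop date is prior to the injection date, then". Only this row uses the stop date.
- **Start time missing.** The time is set to 23:59 and the 48-hour definition is applied.
- **Partial date.** If the day is missing, the rule reads "If AE start month and year are the same as injection date month and year then" TEAE = Y. If the month is missing, a match on year alone gives Y. Neither branch has a stop-date condition.

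Protocol 7.7.2 defines trial-emergent AEs as those arising "after the informed consent, and prior to administration of study drug" and sends them to the AE eCRF, so pre-dose events are in the same data set. Protocol 7.7 asks for stop dates as well as start dates.

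**The concern.** A stop date before injection settles the question: an event that has ended can neither begin nor worsen in the 48 hours after a later injection. The Partial Date row discards that information. The result is also perverse, because knowing the start month or year changes the flag from a correct N to an incorrect Y.

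Expanding the safety database is one of the two primary objectives (SAP 3), and the AE summary tables in SAP 8.5.2 to 8.5.2.6 are built on TEAEs. A wrongly flagged event enters all the tables that apply to it. There it is also subject to the worst-case rules for missing attributes: missing severity becomes severe, missing relationship becomes related, and missing seriousness becomes serious (SAP 8.5.2.1, 8.5.2.2, 8.5.2.4).

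The second matter is one of completeness. The first row covers stop dates after and before the injection date but says nothing of a stop on the date itself. A programmer who meets that record must decide without an instruction from the table.

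**Working it through.** The plan gives no figure to reproduce; the check is a literal trace of Table 4.

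**Inputs.** The rules are those of SAP 8.5.2.7 and the 48-hour definition in SAP 6.6.2. The injection is assumed to be on 20 June 2015 at 10:00; the date is illustrative.

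**Trace.**

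| Start date known | Stop date | Table 4 flag | Flag with the fix |
|---|---|---|---|
| June 2015, day missing | 5 June | Y | N |
| 2015, day and month missing | 10 March | Y | N |
| Nothing | 19 June | N | N |
| Nothing | 20 June | no branch | Y |
| Nothing | 21 June, or missing | Y | Y |
| June 2015, day missing | 20 June | Y | Y |
| 20 June, time missing | 20 June | Y | Y |

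The event in the first line ended 15 days before dosing. With no start information at all, the first row of Table 4 would give N for that same stop date. The two rows therefore disagree, and the one with less information gives the answer consistent with SAP 6.6.2.

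The last two lines show that same-day events are already flagged Y when the partial date matches or when only the clock time is missing. The gap is confined to a wholly missing start date with a stop on the injection date.

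**How far the partial-date rule reaches.** Take every injection day of 2015 and stop dates 1 to 30 days earlier, with the start month and year equal to those of the stop date. The 30 days echo the preferred screening window in Protocol 7.1.1; the even spread of dates is an assumption.

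- Combinations: 365 × 30 = 10,950.
- Day missing: the flag is Y whenever the stop falls in the injection month. A month of d days contributes d(d − 1)/2 cases. For 2015 this is 7 × 465 + 4 × 435 + 378 = 5,373, and 5,373 / 10,950 = 49.1%.
- Month missing: the flag is Y unless the stop falls in the previous year, which happens in 30 + 29 + … + 1 = 465 cases. (10,950 − 465) / 10,950 = 10,485 / 10,950 = 95.8%.
- The correct share in both settings is 0%, since every one of these events ended before dosing.

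These percentages describe how the rule behaves once such a record exists. They are not expected counts.

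**Weight of one subject.** SAP 4.4 gives about 179 dosed subjects, so one subject is 1 / 179 = 0.56 percentage points of a TEAE incidence, and only if that subject has no other TEAE counted at that level of the table.

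**The case against.** The best defence is that the SAP announces a conservative approach and that the Partial Date row errs in the announced direction. It can only add TEAEs, so it hides no signal. It also operates only when three things coincide: a known stop date before injection, an incomplete start date, and a start month or year that matches the injection. Conditions that began before screening go to medical history (Protocol 7.7.2), and monitors check eCRF entries against source (Protocol 10.6), so few such records are likely. All AEs, treatment-emergent or not, appear in a listing (SAP 8.5.2).

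This stands as to size. It does not justify the rule: conservatism is a way to resolve uncertainty, and a recorded pre-dose stop date leaves none. The first row of Table 4 already accepts that reasoning.

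On the second gap, a reader might go further and infer that same-day events are left unclassified, and that acute injection reactions therefore drop out of the TEAE tables. One could point to SAP 7.2, "For situations with no rules for handling missing data the default will be no imputation", and to SAP 4.1.2, "Any subject who experienced an adverse event was not discharged until the event had resolved or stabilized". The documents do not support that inference, for three reasons:

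- Most same-day records are classified Y, as the trace shows.
- Subjects are observed continuously at the imaging visit and seen by a physician before discharge (Protocol 7.1.2). A reaction that begins and ends there has a known onset date; the item likely to be missing is the time, which the second row handles.
- The default in SAP 7.2 applies where no rule exists, and the lead-in to Table 4 arguably supplies one that points to Y. What remains is that the lead-in defers to the table for its detail, and the table omits the case.

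**Conclusion.** The Partial Date row is wrong as written. It gives Y to events that ended before dosing, against SAP 6.6.2 and against the first row of the same table. The missing branch for a stop on the injection date is a narrower drafting gap, limited to records with no start date at all, where the lead-in suggests Y but the table does not say so.

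The effect is probably small. The documents give no count of partially dated AEs, so it cannot be quantified beyond the 0.56 percentage points that a single subject can move. The direction of the partial-date error is known: TEAEs can be over-counted, never under-counted. A reader should not infer that the safety tables are materially unreliable or that events are lost from the report. The case for correction is that a stated rule yields a flag known to be false and is cheap to put right. The conclusion rests on reading Table 4 literally, as a programmer would.

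**What to change.** Make two changes to Table 4 in SAP 8.5.2.7:

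1. Add an opening line: *If the AE stop date is known and is prior to the injection date, TEAE = N regardless of which part of the start date is missing.*
2. Reword the Y condition of the first row: *stop date is missing, or on or after the injection date: TEAE = Y.*

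The second change will also flag an undated event that ended earlier on the injection day, before dosing. That is genuine uncertainty, and Y there agrees with the stated conservative approach.

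The cost is a short SAP edit and a few lines of derivation code. No new data are needed. TEAE counts may differ slightly: down where a pre-dose event is no longer counted, up where an undated same-day event would otherwise have had no flag.
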